Our longitudinal mixed-methods study will use a one-group repeated measures intervention design coupled with qualitative methods to provide a comprehensive view of the feasibility, acceptability, and preliminary effects of the MOMS intervention.^{167,168} Semi-structured interviews, recruitment and retention numbers, and participant logs will be used to evaluate feasibility and acceptability of the intervention (Specific Aim 1). Recently collected archival comparison group data from an existing study described in Section D.2. below will be used to contribute to explorations of preliminary effects of the intervention by comparing longitudinal psychobehavioral data, birth weight data, and genome-wide and gene-specific DNAm data (Specific Aims 2 and 3).

Screening: Interested individuals will contact the study staff via email or phone call. Study staff will call the participant back to conduct screening. Screening will be done by phone in order to minimize burden of individuals, particularly those who may not be eligible. The screening script is uploaded in this application and is focused on the eligibility criteria. (see attached screening scripts document) No screening questionnaire data will be retained.

Following an initial phone interview in which the study will be generally discussed, eligible and interested women will be invited to an in-person meeting at a private and mutually agreed upon location (e.g., private room in School of Nursing or obstetrician♦s office) or a phone meeting (for women who have transportation issues/parenting conflicts) to engage in the consent process with the PI/PD. In this formal consenting process, the potential participants♦ questions will be fully answered. If a woman discusses the consent by phone, she will be emailed or mailed the consent form so that she has time to read it prior to the phone discussion; the research staff member will discuss it extensively with her and, when she is ready, obtain verbal consent. The woman will then sign a hard copy of the Consent Form and receive a copy of the signed form when she meets with the research staff member for the first blood draw/ yoga session.

Intervention: The MOMS intervention incorporates key components informed by the SM^{98,110} and physical activity (PA) literature,^{108,114} as well as our research about the acceptability of yoga as a mode of mindful PA.¹³⁷

Summary of Study Visits:

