
Objective Measures: (a) **Epigenetic (DNAm):** Peripheral blood specimens will be collected at baseline (gestation 12-22 weeks) and intervention week 12 (gestation of 24-34 weeks), as summarized in Table 1. The PD and/or RAs will arrange to meet participants to collect the blood and transport samples to the VCU School of Nursing's lab for DNA extraction.

Samples will be shipped to HudsonAlpha for DNA methylation assays. HudsonAlpha will use the following procedures for DNA methylation: genome-wide methylation patterns will be determined using the 450K HumanMethylation Chip (Illumina) according to the vendor's protocol. Briefly, DNA will be extracted from the blood samples using standard techniques (Puregene Isolation Kit; Qiagen). Following bisulfite conversion of the DNA, the methylation patterns of the 485,764 targets (including CpG islands, shores, open sea) interrogated in the 450K array will be determined. To verify the results of the 450K array for targeted regions of interest, single loci methylation-sensitive studies of bisulfite converted DNA will be conducted using standard methods.²⁰⁵ Gene-specific patterns of candidate genes chosen a priori will be closely examined. All samples will be coded prior to deliver to the testing labs. As methylation patterns vary from tissue to tissue, one concern is if the patterns present in white blood cells are reflective of the relevant cumulative epigenetic changes

involved in chronic depressive symptoms. Skepticism regarding the utility of blood for the assessment of conditions having brain/nervous system components has recently been diminished by the observation that comparable DNAm changes induced by environmental/social events occur in multiple tissues.⁷⁵ Based on these findings, Szyf²⁰⁶ noted that the results of recent investigations demonstrate that it is feasible to study behaviorally related DNA methylation signatures in peripheral cells²⁰⁶ (p.334). Given this supporting data, as well as the practical need to collect a minimally invasive specimen for study in this pregnant population, peripheral blood will be used to assess DNAm patterns. (b) Birth weight: At the postpartum visit, mothers will be asked to report the baby²⁰⁶s birth weight.

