Comparison Group Data: Archival data from an existing IRB-approved study (NIMHD2P60MD002256, PI: [name]) includes pregnant women recruited from the VCUHS and area clinics who did not receive the MOMS intervention yet were followed throughout their pregnancies and into the postpartum period, using psychobehavioral, birth weight, and DNAm measures identical to those proposed in this study. The de-identified data will be used to form two age/race-matched comparison groups: (a) positive comparison group (n=40): pregnant women with clinically relevant depressive symptoms receiving the UC; and, (b) negative comparison group (n=40): pregnant women without clinical depressive symptoms. The timelines of these studies align well; as of May 2015, the study has enrolled approximately 135 women (50% AA) with ~15% of the sample endorsing depressive symptoms (unpublished data). Data collection from the total expected sample (n=220) will be completed by early 2017, at which point the proposed study will be ready to derive the comparison groups for analysis. To facilitate longitudinal comparisons across the two studies, the pre-/post-intervention data for the proposed study will correspond to data collected early in the second trimester of pregnancy (approximately 12-22 weeks gestation) and late in second trimester/ early in third trimester of pregnancy (approximately 24-34 weeks gestation) respectively, in the comparison study, represented in Figure 2.

Data Analysis Plan

Aim 1: Evaluate the feasibility and acceptability of the MOMS intervention for chronic depressive symptoms during pregnancy: (a) Data related to recruitment, retention and adherence to the MOMS intervention will be analyzed using descriptive techniques, including percentages and means. The number of participants who complete each time point will be recorded and percentages of the following calculated: persons eligible to participate; persons who signed a consent form; and PA sessions attended, home PA participation, and participant attrition. Reasons for attrition will be described.

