(a) positive comparison group (n=40): pregnant women with clinically relevant depressive symptoms receiving the UC; and, (b) negative comparison group (n=40): pregnant women without clinical depressive symptoms. The timelines of these studies align well; as of May 2015, the study has enrolled approximately 135 women (50% AA) with ~15% of the sample endorsing depressive symptoms (unpublished data). Data collection from the total expected sample (n=220) will be completed by early 2017, at which point the proposed study will be ready to derive the comparison groups for analysis. To facilitate longitudinal comparisons across the two studies, the pre-/post-intervention data for the proposed study will correspond to data collected early in the second trimester of pregnancy (approximately 12-22 weeks gestation) and late in second trimester/ early in third trimester of pregnancy (approximately 24-34 weeks gestation) respectively, in the comparison study, represented in Figure 2. This analysis is fully described in section D.8.2. Although the lack of a concurrent randomized control group presents a threat to statistical conclusion and internal study validity, the use of this archival comparison group data is important because it contributes rich longitudinal comparison data of extensively phenotyped pregnant women. Further, use of archival comparison group data allows for full exploration of our primary aim (feasibility and acceptability of the pilot MOMS intervention) with a large enough sample size (total n=120; n=40 participants of MOMS intervention; n=40 positive comparison group; n=40 negative comparison group) to also explore preliminary effects, which increases statistical conclusion validity (reducing Type II error), maximizes flexibility in the budget of the R15 mechanism, and contributes important data for the development of future studies.

2. * Describe how you have access to the data/specimens:

[name], co-I on this study, is the PI on the study which will provide the deidentified archival data.

3. *

Describe any identifiers or coded information that will be obtained that can be linked directly or indirectly to the identity of participants:

n/a-- data will be completely deidentified

4. * Did individuals provide consent for research when the data / samples were originally collected?

Yes
 No

5. If yes, did the consent allow for sharing of the data:

Yes
 No

ID: MS8_HM20006941

[View: SF - Internet Data Collection Details](#)

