Following IRB approval, 41 pregnant women at 12-20 weeks gestation will be recruited from the Virginia Commonwealth University Health System (VCUHS) and community obstetric clinics, to participate in the MOMP intervention. Potential participants must be less than 28 weeks pregnant at the time of starting the 12-week prenatal yoga classes. Additional inclusion criteria are as follows: (1) age 18; (2) self-report of depressive symptoms prior to pregnancy; (3) current depressive symptoms at a moderate-to-severe level, as defined by a score ≥ 10 on the Patient Health Questionnaire (PHQ9);¹⁶⁹ (4) able to read, write, and understand English; (5) self-identify as Black/African American (AA) or White (matching demographics of archival data used for comparison groups); (6) absence of suicidal ideations, psychosis, or mania (measured with MINI Neuropsychiatric Interview as a screening tool);¹⁷⁰ (7) absence of pregnancy complications/physical conditions making PA inadvisable;¹²² (8) has not engaged in a consistent mindfulness-based PA routine during the pregnancy (such as yoga or similar activities more than once per month). Data about use of UC for depression (medications, psychotherapy) will be collected at multiple timepoints and included as covariates in analyses.

For the comparison group: Archival data from an existing IRB-approved study (NIMHD2P60MD002256, PI: [name]) includes pregnant women recruited from the VCUHS and area clinics who did not receive the MOMP intervention yet were followed throughout their pregnancies and into the postpartum period, using psychobehavioral, birth weight, and DNA methylation measures

identical to those proposed in this study. The de-identified data will be used to form two age/race-matched comparison groups: (a) positive comparison group (n=40): pregnant women with clinically relevant depressive symptoms receiving the UC; and, (b) negative comparison group (n=40): pregnant women without clinical depressive symptoms.

5. * List the study exclusion criteria:

If individual does not meet the inclusion criteria listed above, they are ineligible for the study.

6. * Check all participant groups that will be included in this study or discernable in the research data/specimens. In particular, if you will know that a regulated vulnerable population (children, pregnant women, or prisoners) is involved in the study, be sure to check them:

Healthy volunteers

Children

Emancipated minors

Pregnant women

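### The class-start limit (below 28 weeks) allows a week-12 assessment as late as 38w6d to 39w6d, outside the 24-34 week window used to align MOMS with the archive

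*Combined protocol and SAP*

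**What the plan says.** Study Population, item 4, sets gestation at entry: "41 pregnant women at 12-20 weeks gestation will be recruited". The same item gives a separate limit for the first class: "Potential participants must be less than 28 weeks pregnant at the time of starting the 12-week prenatal yoga classes".

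Research Description, item 4, Objective Measures (a), fixes the timing of the blood samples: "Peripheral blood specimens will be collected at baseline (gestation 12-22 weeks) and intervention week 12 (gestation of 24-34 weeks". The Comparison Group Data paragraph, repeated in Existing Data/Specimen Details, item 1, explains why timing matters: "the pre-/post-intervention data for the proposed study will correspond to data collected early in the second trimester of pregnancy" (approximately 12-22 weeks) and, for the second point, "late in second trimester/ early in third trimester of pregnancy (approximately 24-34 weeks gestation) respectively, in the comparison study".

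On matching, the plan says: "The de-identified data will be used to form two age/race-matched comparison groups". The Aim 2 mixed model has Group, Time (BL, IW6, IW12, PP) and their interaction. Covariates are left to be explored. Usual care for depression is the one named, and gestational age is not mentioned. Aim 3 step (c) compares methylation across the three groups.

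**The concern.** The start limit and the week-12 window are both stated rules, and they do not fit together. There is no concurrent control group, so comparable gestation is one of the features on which the MOMS-versus-archive contrasts depend. For a woman who starts classes late, the visit labelled IW12 would set late third-trimester MOMS data against archive data from 24-34 weeks. This would enter the Aim 2 contrast at week 12 and the Aim 3 step (c) comparison, and through Aim 2 the effect sizes meant to guide future studies.

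There is also a missing-data side. Visit 14 is defined as the last visit in pregnancy. If it falls due at 38w6d to 39w6d, some women may already have delivered, so missing week-12 data could depend on how late a woman started.

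**Working it through.** **Inputs.** Recruitment at 12-20 weeks and class start below 28 weeks, so 27w6d at the latest (Study Population, item 4). Baseline at 12-22 weeks and week 12 at 24-34 weeks (Objective Measures; Comparison Group Data). Twelve weekly classes at visits 2 to 13, and visit 7, which is the sixth class, labelled Intervention Week 6 (study visit summaries). That label shows that intervention weeks run from the first class. The twelfth class therefore falls 11 weeks after the first, and an assessment after 12 full weeks falls 12 weeks after it.

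**The plan's own window.** Baseline plus 12 weeks: 12 + 12 = 24 and 22 + 12 = 34. The 24-34 week window is reproduced exactly, and it assumes that classes begin at about the time of baseline.

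**Latest week 12 that the start rule allows.**
- Twelfth class: 27w6d + 11w = 38w6d.
- Twelve full weeks: 27w6d + 12w = 39w6d.

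**Overshoot and the latest start that keeps the window.**

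| Upper edge read as | Week 12 read as | Overshoot | Latest start inside window |
|---|---|---|---|
| 34w0d | 12 full weeks | 39w6d - 34w0d = 5w6d | 34w0d - 12w = 22w0d |
| 34w6d | 12 full weeks | 39w6d - 34w6d = 5w0d | 34w6d - 12w = 22w6d |
| 34w0d | twelfth class | 38w6d - 34w0d = 4w6d | 34w0d - 11w = 23w0d |
| 34w6d | twelfth class | 38w6d - 34w6d = 4w0d | 34w6d - 11w = 23w6d |

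**Wait needed to reach the extreme.** From baseline at 22w0d: 27w6d - 22w0d = 5w6d. From recruitment at 20w0d: 27w6d - 20w0d = 7w6d. A woman recruited at 20w0d who starts at once reaches week 12 at 31w0d to 32w0d, well inside the window.

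**Who would be affected by a fixed delay.** The recruitment gestation above which a woman leaves the window is the latest start minus the delay. The delays are assumptions, because the documents give none; recruitment is taken to end at 20w0d.

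| Delay to first class | Strict (start by 22w0d) | Most lenient (start by 23w6d) |
|---|---|---|
| 2 weeks | 20w0d: nobody | 21w6d: nobody |
| 4 weeks | after 18w0d | after 19w6d |
| 6 weeks | after 16w0d | after 17w6d |

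**Cost of a restricted analysis.** Suppose the 20-40% attrition in the sample-size section, which is general experience from other studies, applied at week 12. Then 41 × 0.6 = 24.6 to 41 × 0.8 = 32.8, or about 25 to 33 women, would have week-12 data. The section's minimum of 12 observations would still be met unless more than 25 - 12 = 13, or 33 - 12 = 21, were excluded. As an illustration only, suppose five were excluded. The 95% half-width of a MOMS week-12 mean, t(0.975, n-1)/√n in SD units, would go from 0.413 (n = 25) to 0.468 (n = 20), 13% wider, or from 0.355 (n = 33) to 0.388 (n = 28), 9% wider.

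**The case against.** The strongest reply is that the 28-week rule is only an outer limit. The plan as a whole points to a prompt start: recruitment ends at 20 weeks, the baseline-plus-12 arithmetic assumes it, and the consent procedure has the woman sign "when she meets with the research staff member for the first blood draw/ yoga session". The Study Visit #1 text likewise has the project director begin the intervention once baseline is done. No text plans a wait of six to eight weeks. This stands, and it is why the number affected may be zero. It does not remove the conflict: no text that could be read caps the gap between baseline and first class, and the only explicit limit on the start is 28 weeks.

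A second reply is that the windows are approximate. In the comparison-group text they are; the blood-sample text has no such qualifier. An overshoot of 4w0d to 5w6d is more than rounding, and 38-39 weeks is not early third trimester.

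A third reply is that unseen material may deal with this. Figure 2 and Table 1 cover the time points, and of the archive comparison the plan says "This analysis is fully described in section D.8.2", a section that was not available. This also stands, and no claim can be made that the full plan lacks a rule.

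Finally, gestation is not the only basis for comparability. The plan also relies on age and race matching, identical measures and two comparison groups. It already concedes that the lack of a concurrent randomized control threatens validity, it is a pilot not powered for effectiveness, and its open covariate list would permit adjustment. All of that limits the weight of the point.

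**Conclusion.** The conflict between the start limit and the week-12 window is real, and it is worth removing because doing so is cheap. Its possible size is an overshoot of up to 4w0d to 5w6d for an individual woman. Its actual size depends on start delays, which the documents do not give.

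A reader might infer more: that MOMS week-12 data will be collected at 38-39 weeks, or that the comparison with the archive is biased to a known degree. The documents support neither. The late dates are the permitted extreme, delays of two weeks or less put nobody outside the window, and no weekly trend in symptoms or methylation is given from which a bias or its direction could be worked out. Nor does the point reach the feasibility and acceptability aim.

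The paired pre/post test in Aim 3 step (b) is a separate matter. It mixes intervention with advancing gestation for every woman, and a tighter start limit would not change that.

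The conclusion rests on counting intervention weeks from the first class, as the visit 7 label implies, and on the absence of a visit window or maximum gap in Figure 2, Table 1 or section D.8.2.

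**What to change.** 1. In Study Population, item 4, set a class-start limit consistent with 24-34 weeks, that is, a start by about 22-23 weeks. If later starts must be kept for recruitment, restate the week-12 window that the rule gives (up to 38w6d to 39w6d). The choice is clinical and practical. If recruitment has already closed, only restating the window and the next two steps apply.
2. Derive gestational age at each MOMS prenatal assessment from the self-reported gestational age (HIPAA, item 1) and the visit date. Report its distribution at week 12 and the number of deliveries before visit 14.
3. Add a sensitivity analysis of the MOMS-versus-archive week-12 contrasts in Aim 2 and Aim 3 step (c). Drop only the week-12 records outside 24-34 weeks, keep those women's other records, and give the number dropped. Report it beside the intent-to-treat result, not in its place.

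A time-varying gestational-age covariate in the Aim 2 model is not advised. It is undefined at the postpartum level of Time, and within MOMS it is nearly collinear with Time.

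The cost is one protocol sentence, one derived variable from data already collected, and one extra analysis. The downside is a slightly narrower start window, or a somewhat smaller sensitivity sample that favours women who started promptly.

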Individual and Environmental Factors: A study-specific demographic and health history form, as used in the study contributing archival comparison data, will be administered at the baseline visit which includes questions about age, socioeconomic status, educational attainment, lifestyle behaviors (exercise), demographics, current use of depression UC (e.g., psychotherapy, antidepressants, other psychiatric medications), current and past medical history, number of lifetime depressive episodes, and current major life events. Social support will be measured with the MOS Social Support Survey (MOS)¹⁷⁴ which assesses emotional, tangible, affectionate, and positive social interactions. With a possible score of 20-100, a higher score on the MOS represents more social support. A history of major life stresses in the form of traumatic events will be measured with the Trauma History Questionnaire (THQ).^{177,178} The 24-item THQ is an inventory of potentially traumatic events that have been associated with increased risk for depressive symptoms;¹⁹⁹⁻²⁰¹ the THQ

generates a total score representing the numbers and types of traumatic events experienced by the individual.

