(a) **Depressive symptom severity:** Depressive symptom severity will be evaluated using the Patient Health Questionnaire (PHQ-9), a widely used instrument which has been validated during pregnancy.¹⁶⁹ The PHQ-9 includes self-report items regarding depressive symptoms over the past two weeks. Total scores range from 0-27: 0-4 indicates minimal depression, 5-9 mild depressive symptoms, 10-14 moderate depressive symptoms, 15-19 moderately severe depressive symptoms, and =20 severe depressive symptoms. For analysis purposes, presence of depressive symptoms will be defined as a score =10 on the PHQ9. The PHQ-9 includes a question on suicidal ideation,^{202,203} which will be used for monitoring for adverse events as described in the Protection of Human Subjects section. Because the archival comparison group database includes the Edinburgh Postnatal Depression Scale (EPDS)¹⁸⁰ in the pregnancy and postpartum assessment, we will also administer this survey at the same timepoints. The EPDS is a widely used and validated measure of depressive symptoms, with 10 questions appropriate for the prenatal and postpartum woman; a score =10 (range 0-30) suggests possible depressive symptoms. Guidelines regarding management of participants with depressive symptoms or suicidal thoughts are detailed in the Protection of Human Subjects section but in brief, the researchers will be poised to assess further and make referrals to appropriate community organizations, healthcare providers, or emergency departments in cases of psychological distress (score =20 on PHQ9 and/or suicidal ideation) or physical injury. (b) **Stress:** The Perceived Stress Scale-10 (PSS-10), a widely used, psychometrically sound instrument, will assess the degree to which a participant perceives stress in her life during the past month.¹⁸¹⁻¹⁸⁵ The PSS-10 asks respondents to report about feelings such as unpredictability, uncontrollability, and overloading of stress in their lives; scores range from 0-40; higher scores correspond to a higher perceived stress level.¹⁸⁴ (c) **Anxiety:** Current levels of anxiety (state anxiety) will be evaluated with the State-Trait Anxiety Inventory, Form Y (STA). This study focuses specifically on state anxiety, as this score is sensitive to women's anxiety during pregnancy and is more likely to demonstrate change within an intervention period.^{190,204} This measure yields reliable and valid scores.¹⁸⁷⁻¹⁸⁹ The STA scores range from 20-40, with higher scores representing higher levels of state anxiety. (d) **Rumination:** Rumination, or repetitive self-critical thinking, will be evaluated with the 10-item Ruminative Responses Scale (RRS) which assesses the propensity to ruminate in association with sadness or depression. A psychometrically sound and widely used instrument, the RRS asks respondents to rate how often they experience various aspects of rumination.¹⁹³ The RRS has two factors of brooding (self-critical pondering) and reflecting (emotionally-neutral pondering or brainstorming). (e) **Self-Efficacy for Physical Activity:** The Physical Activity Self-Efficacy Scale (PASES)^{194,195} is an eight question scale which contains items about SM of physical activities and social support regarding PA. This psychometrically sound scale was selected because of its specific focus on SM of PA. Originally designed for adolescents, the wording has been slightly adapted for an adult sample. (f) **Maternal-Fetal/Child Attachment:** The Maternal-Fetal Attachment Scale (MFAS)^{32,198} assesses the extent to which women have an affiliation and interaction with their unborn child (during pregnancy) and their infant (during PP). Maternal depression has a proximal effect on maternal-child attachment,¹⁷ hence it is highly relevant to evaluate attachment in relation to an intervention designed to address depression.

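### Two MOMS entry exclusions (criteria 6 and 8) have no stated counterpart for the depressed archival group, so the Aim 2 contrast compares women under different stated eligibility rules

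*Combined protocol and SAP*

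**What the plan says.** Study Population, item 4, lists the MOMS entry criteria. Criterion (6) is "absence of suicidal ideations, psychosis, or mania", screened with the MINI. Criterion (8) is that the woman "has not engaged in a consistent mindfulness-based PA routine during the pregnancy", with yoga or similar more than once a month given as the example.

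The comparison groups are described in three places: Comparison Group Data (Research Description, item 4), Existing Data/Specimen Details (item 1), and Study Population (item 4). Each says "The de-identified data will be used to form two age/race-matched comparison groups". The positive group is 40 women with relevant depressive symptoms who receive usual care. The archival study's own entry criteria are not given.

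The Aim 2 analysis names the PHQ-9 as its main variable and fits a mixed model with group, time and their interaction. Usual care is the only covariate named, there and in Study Population, item 4.

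Three further statements bear on what can be repaired:
- Under Maternal Psychological Measures (a), "The PHQ-9 includes a question on suicidal ideation".
- The demographic and health history form is described "as used in the study contributing archival comparison data". It covers medical history, psychiatric medication, number of depressive episodes and exercise.
- Comparison Group Data calls the measures in the two studies identical. Maternal Psychological Measures (a), however, names only the EPDS as a depression scale in the archive.

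**The concern.** When an external group stands in for a control, the usual first step is to apply the trial's entry rules to it. The plan accepts this principle for race: criterion (5) restricts MOMS so that it matches the archive. It does not say the same for criteria (6) and (8), and each could affect the contrast in its own way.

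Criterion (6) selects on something close to the outcome, because suicidal ideation is part of the PHQ-9. Women with ideation, psychosis or mania may also follow a different course over pregnancy. Change from baseline removes a constant gap between groups but not a different trajectory, and trajectory is what the group-by-time term estimates.

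Criterion (8) keeps out of MOMS women who already practise its central activity. Any such women in the archive would be partly exposed, and the contrast would shrink.

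Aim 2 exists to supply effect sizes for later studies. A biased estimate would carry straight into the design of the next trial.

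**Working it through.** **1. Is either criterion covered elsewhere?**

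| Route | What the plan states | Covers (6)? | Covers (8)? |
|---|---|---|---|
| Definition of the positive group | Symptoms, receipt of usual care | No | No |
| Matching | Age, race | No | No |
| Covariates | Usual care | No | No |
| Stated limitation (Existing Data/Specimen Details, item 1) | No concurrent randomized control | Not mentioned | Not mentioned |

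**2. How many depressed archival women are there before any filter?** Inputs from Comparison Group Data: 220 women expected, about 15% with depressive symptoms.

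- 220 × 0.15 = 33, against the stated 40.
- At 13% the count is 28.6; at 17% it is 37.4. Reaching 40 needs 40/220 = 18.2%.

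The stated 40 is therefore not reproduced from the plan's own inputs. The 33 is also before the usual-care requirement and the matching.

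**3. How large could the bias be?** The documents give no rate of suicidal ideation, psychosis, mania or yoga use in the archive, so everything in this step is assumed.

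Shift in the comparison mean = (share who would fail the criteria) × (their mean difference in SD):
- 0.05 × 0.5 = 0.025 SD at the low end
- 0.30 × 1.0 = 0.30 SD at the high end

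For the yoga route, shrinkage = (share already practising) × (fraction of the MOMS effect they obtain). With 10-20% practising, shrinkage is at most 10-20%, reached only if they obtain the whole effect. That is an extreme case, because MOMS also includes the nurse partnership and self-directed home activity.

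**4. What is that measured against?** The 95% half-width of a two-group mean difference, in SD units, is t × √(1/n₁ + 1/n₂):
- 40 v 40: 0.445
- 40 v 33: 0.469
- 32 v 33 (20% MOMS attrition): 0.496
- 24 v 33 (40% MOMS attrition): 0.538

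The assumed shift is smaller than the sampling uncertainty, but unlike that uncertainty it does not average out.

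**5. What does filtering cost?** Assume 10-20% of the 33 are lost, leaving 33 × 0.9 = 29.7 or 33 × 0.8 = 26.4. Relative width = √(1/n₁ + 1/n₂) ÷ √(1/n₁ + 1/33):
- n₁ = 24: 1.023 to 1.051
- n₁ = 32: 1.027 to 1.060
- n₁ = 40 (no attrition): 1.030 to 1.066

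At the plan's 20-40% attrition the interval is about 2-6% wider. With no attrition the upper end is nearer 7%.

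**The case against.** The strongest reply is that much of what a reader might infer is not in the documents. This largely stands.

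- A reader might infer that the archival group is unfiltered. The archival study's entry criteria are not in the text, and it may have had psychiatric exclusions of its own. What is supported is that no equivalent filter is stated.
- A reader might say the group is formed on symptoms, age and race alone. Receipt of usual care is also part of its definition.
- A reader might infer that MOMS women start at zero on the PHQ-9 ideation item. Criterion (6) is measured with the MINI at screening, and the plan treats the MINI and the PHQ-9 item as separate instruments, so a zero score is not guaranteed.
- A reader might conclude that usual care is made to look worse and MOMS better. Criterion (3) sets no upper PHQ-9 limit, so MOMS keeps severe depression, and the yoga route works the other way.

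A second reply is that the data for a filter may not exist. The history form is not described as asking about psychosis, mania or yoga, and PHQ-9 data in the archive rest on the statement that measures are identical. This also stands, and it makes the filter conditional on what is held. Even then, a PHQ-9 item is not the same test as the MINI.

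A third reply is that this is a pilot which disclaims power and already admits a threat to validity. That does not answer the point. The admitted threat is the absence of randomization. Unequal eligibility is a separate problem and can be reduced with data that may already be in hand.

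Finally, criteria (2) and (7) are not stated for the archive either, so one eligibility statement could settle all of them. That is a reason to make the repair once, not to omit it.

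**Conclusion.** The concern holds in a limited form. Criteria (6) and (8) govern entry to MOMS. No equivalent is stated for the depressed archival group, and neither the matching nor the named covariate makes up for it. Followed as written, the plan contrasts groups with different stated eligibility.

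The documents do not establish that the groups actually differ on these features, nor the sign or size of any bias. The 0.025-0.30 SD range rests wholly on the assumed shares and differences. The consequence is a possibly biased planning estimate, not a wrong confirmatory test. The change should be made because it is standard practice for external comparators and costs little precision. Confidence is medium, because the archive's own criteria and items are not visible.

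**What to change.** In the comparison-group text:

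1. State the archival study's own eligibility criteria.
2. When deriving the positive group, apply criteria (6) and (8) at the early second-trimester visit wherever the archive holds a usable item. That means the PHQ-9 suicidal-ideation item, once it is confirmed that the archive holds the PHQ-9, and the history and exercise items if they capture psychosis, mania or yoga.
3. Make the filtered contrast the main Aim 2 contrast and show the unfiltered one as a sensitivity analysis.
4. Report how many depressed women remain after each step, starting from the roughly 33 that the plan's figures imply.
5. Name any criterion that cannot be applied as a limitation of the reported effect size.

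The cost is a filter and a short count table on archival data, plus a smaller comparison group with the modest widening shown above. The usual-care requirement, the matching and any further criteria would reduce the group again, so the final count should be known before the analysis is fixed.
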